10.2 Clinical Laboratory Evaluation

Absolute values and changes from Baseline of clinical laboratory data (hematology, chemistry, continuous urinalysis parameter, and lipids) will be summarized with descriptive statistics at Baseline, and Week 28 (i.e., Part 1, and through Week 52 and Week 72 for the final analysis. For the laboratory values which have the normal range (e.g., below/within/above the normal range) or categorical result (e.g., ¬/±/+), a shift table will display the cross tabulation of the Baseline result category versus the result of the post-treatment period at each visit according to the study part being reported.

All clinical laboratory data relevant to the reporting period (i.e., Part 1 or overall) will be listed by subject. Values outside the normal ranges will be flagged. Flags will describe direction relative to normal range in relevant parameters.

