1.3 Schedule of Activities

Table 1: Schedule of Activities

	Screening		1		PART 3											
		Double-blind Placebo-controlled									Double-blind Active Treatment					
Week		0	4	8	12	16a	20	24	28 ^b	32	36	40	44	52°	72	
		(Baseline)												EoT	EoS	
Visit Number	1	2	3	4	5	6	7	8	9	10	11	12	13	14	15	
Day	Within 28	1	+/-	+/-	+/-	+/-	+/-	+/-	+/-	+/-	+/-	+/-	+/-	+/-	+/-	
	Days		3 days	3 days	7 days	7 days	7 days	7 days	7 days							
Written informed consent	X															
Inclusion/Exclusion criteria	X	X ^d														
Demographic information	X	Xe														
Physical examination	X	X												X	X	
Vital signs	X	X	X	X	X	X	X	X	X	X	X	X	X	X	X	
AEf/Concomitant medications	X	X	X	X	X	X	X	X	X	X	X	X	X	X	X	
Medical/ Medication history	X															
Chest X-ray ^g	X															
QuantiFERON ^h	X															
HIV, HbsAg, and HCV serology	X															
ECG		X												X		
Randomization ⁱ		X														
IWRS entry	X	X	X			X			X	X		X	X	X	X	
Study treatment administration ^j		X	X			X			X	X		X	X	X		
Hematology/chemistry/Urinalysisk	X ^l	X							X					X	X	
Lipids ^k		X							X					X		
Serum pregnancy test	X													X		
Urine pregnancy test ^m		X	X	X	X	X	X	X	X	X	X	X	X	X		
C-SSRS ⁿ	X	X	X	X	X	X	X	X	X	X	X	X	X	X		
Efficacy assessments	X	X	X	X	X	X	X	X	X	X	X	X	X	X		
(ViSENPsO, NAPSI, mNAPSI,																
PGA-S, pain NRS, BSA, and																
PASI) ^{o, p}																
s-PGA ^q	X	X				X			X							
CGIS	X	X			X				X		X			X		

	Screening	PART 1 Double-blind Placebo-controlled							Dou	PART 3 OSFU					
Week		0 (Baseline)	4	8	12	16ª	20	24	28 ^b	32	36	40	44	52° EoT	72 EoS
Visit Number	1	2	3	4	5	6	7	8	9	10	11	12	13	14	15
Day	Within 28	1	+/-	+/-	+/-	+/-	+/-	+/-	+/-	+/-	+/-	+/-	+/-	+/-	+/-
	Days		3 days	3 days	7 days	7 days	7 days	7 days	7 days						
CGIC					X				X		X			X	
DLQI and NAPPA-QoL		X			X				X		X			X	
PGIS	X	X			X				X		X			X	
PGIS-P	X	X			X				X		X			X	
PGIC					X				X		X			X	
PGIC-P					X				X		X			X	

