- i. Following completion of Baseline assessments and confirmation that all inclusion/exclusion criteria have been met.

Tildrakizumab

- j. All study procedures of Baseline should be completed prior to study treatment administration. Following randomization, study treatment administration will begin on Day 1 of Week 0, Week 4, Week 16, and Week 28. At Week 28, subjects initially randomized to placebo will be switched over to receive tildrakizumab 100 mg at Weeks 28, 32, and 44. Subjects initially randomized to tildrakizumab 100 mg will continue to receive the active drug at Weeks 28, 40, and 52. In order to maintain blind, subjects who were initially randomized to placebo will receive matching placebo injections at Weeks 40 and 52, while subjects who were initially randomized to tildrakizumab will receive matching placebo injections at Weeks 32 and 44. Study treatment will be administered after performing all study-specific procedures for a particular visit.
- k. Blood samples are to be collected (pre-SC dose where applicable), after ECG and vital signs measurements. At visits where lipids are to be assessed, the blood samples are to be collected (pre-SC dose where applicable) after at least 12 hours fasting, following ECG and vital signs measurements. The following parameters will be reported at Screening only: Serum pregnancy, hepatitis B, hepatitis C, and HIV.
- 1. Subjects with fungal nail infection whose fungal culture will be sent to the laboratory would have a Screening Period of 6 weeks.
- m. Urine pregnancy tests will be performed at the study center using materials supplied by the central laboratory.
- n. The subjects will be assessed for suicidal ideation and behavior at Screening using Screening C-SSRS, at Baseline, using Baseline C-SSRS, and each subsequent visit using the C-SSRS Since Last Visit version as specified in SoA.
- o. The efficacy assessments, ViSENPsO, NAPSI, mNAPSI, PGA-S, BSA, and PASI will be assessed at each visit during the study, starting at the Screening visit. Nail pain NRS will be based on the average score from 7-daily records at Baseline (if average of at least 4 out of the 7 daily recall observations in the week prior to baseline) and single-day recording at Screening.

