9.4.2.1 Adverse Events and Serious Adverse Events

Treatment-emergent adverse events are defined as AEs that first occurred or worsened in severity after the first administration of study treatment.

Adverse events will be coded using the most current version of the Medical Dictionary for Regulatory Activities (MedDRA). For each study treatment, the numbers of TEAEs and incidence rates will be tabulated by preferred term and system organ class.

Treatment-emergent AEs by maximum severity, TEAEs by relationship to study treatment, SAEs, TEAEs leading to death, and TEAEs leading to discontinuation of study treatment will be tabulated for each treatment arm. Commonly occurring TEAEs, i.e., those that occur in 5% or more of the subjects in either treatment arm, will be summarized using descriptive statistics.

The safety of tildrakizumab will be evaluated and reported as the percentage of subjects for the following TEAEs:

- Incidence, seriousness, and severity of all AEs, death cases, and discontinuations from the study.
- Percentage of subjects with severe infections, defined as any infection meeting the regulatory definition of an SAE or any infection requiring IV antibiotics whether or not reported as a serious event as per the regulatory definition.
- Percentage of subjects with malignancies (excluding carcinoma in situ of the cervix).
- Percentage of subjects with non-melanoma skin cancer.
- Percentage of subjects with melanoma skin cancer.
- Percentage of subjects with MACE (see Section 8.3.6).
- Percentage of subjects with study treatment-related hypersensitivity reactions (e.g., anaphylaxis, urticaria, angioedema, etc.).
- Percentage of subjects with injection site reactions (e.g., pain, erythema, edema, etc.).

9.4.2.2 Physical Examinations, 12-Lead ECG, Vital Signs, and Clinical Safety Laboratory Tests (Hematology, Biochemistry, and Urinalysis)

Summaries and listings of data for physical examination findings, vital signs, hematology, biochemistry, and urinalysis laboratory tests will be presented. Appropriate descriptive statistics will be presented for the observed value at each scheduled assessment and for the corresponding change from Baseline.

For hematology and biochemistry tests, listings of subject data will also flag any abnormal or out-of-range values. Clinically significant changes in the laboratory test parameters will be summarized and listed. Hematology and clinical laboratory data will be reported using Conventional Units.

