Appendix 2: Clinical Laboratory Tests

- The tests detailed in Table 7 will be performed by the ACM Global Laboratories. The time points are specified in the Schedule of Activities (SoA) (see Section 1.3).
- Local laboratory tests will be allowed in the event that the central laboratory results will not be available immediately and the Investigator needs to take an immediate decision for any safety concerns. If a local sample is required, it is important that the sample for central analysis is obtained at the same time.
- Local laboratory results must be entered into the eCRF.
- Urine pregnancy test will be performed at the study center prior to study treatment administration.
- Protocol-specific requirements for inclusion or exclusion of subjects are detailed in Section 5.0 of the protocol.
- Additional tests may be performed at any time during the study as determined necessary by the Investigator or required by local regulations.
- Investigators must document their review of each laboratory safety report.

Table 7: Protocol-required Safety Laboratory Assessments

Laboratory Assessments	Parameters		
Hematology	Hemoglobin	White Blood Cell Count (WBC)*	
	Hematocrit	* WBC with Differential only if WBC is abnormal	
	Platelet count		
Clinical Chemistry	Alanine aminotransferase (ALT)	Creatinine	
	Albumin	Gamma glutamyl transferase (GGT)	
	Alkaline phosphatase (ALP)	Glucose	
	Aspartate aminotransferase (AST)	Potassium	
	Bicarbonate	Phosphate (Inorganic)	
	Bilirubin (Total)	Protein (Total)	
	Bilirubin (Direct-only if the total is elevated)	Sodium	
	Calcium	Blood urea nitrogen (urea)	
	Chloride	Creatine Kinase	
	Uric acid	Triglycerides	
	Lactate dehydrogenase		
Lipids (fasting)	Total Cholesterol (fractions)	Triglycerides	
Serum pregnancy a	Human chorionic gonadotropin (hCG) pregnancy test (as needed for women of childbearing potential)		
Follicle-stimulating hormone (FSH)	As needed in a postmenopausal woman amenorrhea without an alternative med	n aged over 45 years with at least 1 year of dical cause.	

Laboratory Assessments	Parameters	
Urinalysis	Bilirubin	рН
	Blood	Protein
	Glucose	Specific gravity
	Ketones	Urobilinogen
	Leukocyte esterase (if it is abnormal, a full microscopic examination may be performed)	Microbiology (At the discretion of Investigator based on urinalysis results)
	Nitrites	Microscopy (At the discretion of Investigator based on urinalysis results)
Viral serology ^a	Hepatitis B surface antigen	
	Hepatitis C Antibody	
	HIV antibodies	

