Tuberculosis (TB) Screening ^a	QuantiFERON® test	

NOTES:

- ^a Only during Screening
- The results of each test must be entered into the electronic case report form (eCRF). The date and exact time of sample collection must be recorded.
- Blood samples are to be collected (prior to study treatment administration), after an electrocardiogram (ECG) and vital sign measurements. At visits where lipids are to be assessed, the blood samples are to be collected (prior to study treatment administration) after 12 hours fasting, following ECG and vital sign measurements.

Appendix 3: Adverse Events: Definitions and Procedures for Recording, Evaluating, Follow-up, and Reporting

Definition of AE

An AE is any untoward medical occurrence in a patient or subject, temporally associated with the use of study treatment, whether or not considered related to the study treatment.

NOTE: An AE can therefore be any unfavorable and unintended sign (including an abnormal laboratory finding), symptom, or disease (new or exacerbated) temporally associated with the use of study treatment.

Events Meeting the AE Definition

- Any abnormal laboratory test results (hematology, clinical chemistry, or urinalysis) or
 other safety assessments (e.g., ECG, radiological scans, vital signs measurements),
 including those that worsen from Baseline, considered clinically significant in the
 medical and scientific judgment of the Investigator (ie, not related to progression of
 underlying disease).
- Exacerbation of a chronic or intermittent pre-existing condition including either an increase in frequency and/or severity of the condition.
- New conditions detected or diagnosed after study treatment administration even though it may have been present before the start of the study.
- Signs, symptoms, or the clinical sequelae of a suspected drug-drug interaction.
- Signs, symptoms, or the clinical sequelae of a suspected overdose of either study treatment or a concomitant medication. Overdose per se will not be reported as an AE/SAE unless it is an intentional overdose taken with possible suicidal/self-harming intent. Such overdoses should be reported regardless of sequelae.

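### Glucose and triglycerides are drawn at Week 72 with no fasting rule, yet SAP 10.2 reports their change and shift from a Baseline sampled under a 12-hour fast

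*SAP*

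**What the plan says.** **Fasting rule.** Footnote k to the Schedule of Activities (protocol 1.3) makes the fast conditional: "At visits where lipids are to be assessed, the blood samples are to be collected (pre-SC dose where applicable) after at least 12 hours fasting". The notes to Table 7 in Appendix 2 carry the same condition: "At visits where lipids are to be assessed, the blood samples are to be collected (prior to study treatment administration) after 12 hours fasting". Neither sets a fast for chemistry as such.

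**Visits.** The Schedule of Activities marks hematology, chemistry and urinalysis at Screening, Baseline, Week 28, Week 52 and Week 72. It marks lipids at Baseline, Week 28 and Week 52 only.

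**Panels.** Table 7 lists glucose under Clinical Chemistry. "Triglycerides" appears there too, and again in the lipid panel. Only the lipid panel is labelled as fasting.

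**Analysis.** SAP 10.2 covers "Absolute values and changes from Baseline of clinical laboratory data (hematology, chemistry, continuous urinalysis parameter, and lipids" and gives the time points as "descriptive statistics at Baseline, and Week 28 (i.e., Part 1, and through Week 52 and Week 72 for the final analysis". It adds shift tables of the Baseline category against the result at each visit. Protocol 9.4.2.2 is as broad: "Appropriate descriptive statistics will be presented for the observed value at each scheduled assessment and for the corresponding change from Baseline". SAP 2.3.4, however, defines the laboratory change-from-Baseline endpoint only as far as Week 52.

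**The concern.** A change from Baseline is interpretable when both samples are taken under the same conditions. At Weeks 28 and 52 the fasting rule matches that at Baseline. At Week 72 it does not, and nothing in SAP 10.2 separates, flags or restricts the two analytes for which this matters.

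Week 72 is also a visit where the reader has little else to lean on. Subjects randomised to placebo who continue are switched to tildrakizumab at Week 28, so by the end of follow-up there is no placebo contrast among continuing subjects. Within-subject change and normal-range shifts carry the interpretation, and those are the outputs exposed to a change in sampling conditions. The same values could also feed the summary of treatment-emergent abnormal laboratory values in protocol 9.4.2.2 and the out-of-range flags in SAP 14.2, unmarked.

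**Working it through.** The plan gives no figure to reproduce. The check sets the visit schedules side by side.

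| Visit | Chemistry (with glucose and triglycerides) | Lipids | Fast required | Summarised in SAP 10.2 |
|---|---|---|---|---|
| Screening | yes | no | no | no |
| Baseline (Week 0) | yes | yes | yes | yes |
| Week 28 | yes | yes | yes | yes |
| Week 52 | yes | yes | yes | yes |
| Week 72 | yes | no | no | yes |

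Sources: Schedule of Activities rows for chemistry and lipids, footnote k, Table 7 and its notes, SAP 10.2.

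1. Post-baseline visits summarised for chemistry: {28, 52, 72}. Visits with a required fast: {0, 28, 52}. Week 72 alone is in the first set and not in the second, so one of three post-baseline summary visits is affected.

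2. Analytes affected: glucose and triglycerides. The protocol itself treats triglycerides as needing a fast, by listing them in the fasting lipid panel. That glucose also depends on recent food intake is general knowledge and is taken here as an assumption.

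3. Form of the artefact. Let f be the share of subjects who attend Week 72 unfasted, and d the mean difference between an unfasted and a fasted value of one analyte. Then

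 mean observed change at Week 72 = mean true change + f × d.

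 At Weeks 28 and 52 the extra term is zero if the fasting rule is followed. At Week 72 it is zero only if f = 0. The documents give neither f nor d, so the term cannot be evaluated. The two analytes would also need separate values of d.

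4. Between arms the extra term is f(A) × d(A) − f(B) × d(B). It is close to zero if attendance habits and food response are similar in the two arms. The exposure is therefore in within-subject change and shifts, not in the arm difference.

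5. Related inconsistencies. SAP 2.3.4 stops the laboratory change endpoint at Week 52 while SAP 10.2 runs to Week 72. SAP 10.2 also names lipids in a summary running to Week 72, although the Schedule of Activities collects none then.

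6. Baseline fallback. SAP 3.2 takes the last value before first dose. If the Day 1 sample is missing, the Screening chemistry value becomes Baseline, and Screening has no fasting rule either.

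**The case against.** The strongest reply is that little depends on this. Safety is analysed descriptively, with no test on laboratory data. Neither analyte is named as an event of special or clinical interest. The rule is the same in both arms. Under protocol 8.2.7 the investigator judges clinical significance, and clinically significant abnormal values are repeated, so a single normal-to-high shift would not stand alone. Every visit within the endpoint of SAP 2.3.4 falls under the fasting rule. All of this stands, and it sets the scale of the point.

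A second reply is that a fasting instruction or a table footnote may sit elsewhere. Protocol 8.2.7 refers to a Laboratory Manual, and SAP section 14 says some table rules are in the mock-ups. Neither was supplied. This is a fair limit: the point holds for the protocol and SAP text only.

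Three stronger readings are tempting and are not supported:

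- A reader might infer that Week 72 values are non-fasting. The documents show only that no fast is required; some or all subjects may attend fasted.
- A reader might put a percentage on the spurious change. With no source for f or d, that would be arithmetic on invented inputs.
- A reader might count Screening as a second affected visit. Screening is not a summary visit in SAP 10.2. It enters only as a fallback Baseline, which should be rare because footnote j requires Baseline procedures to be completed before dosing.

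The reply does not remove the mismatch. SAP 10.2, as written, sets a Baseline sampled under a fasting rule against a sample with no such rule, and its tables would not show it.

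**Conclusion.** The point holds in a limited form. At Week 72 alone, change from Baseline and normal-range shift for glucose and triglycerides can partly reflect sampling conditions. The size cannot be derived from the documents and could be nil if subjects attend fasted. The consequence is confined to a descriptive safety summary of two analytes at one follow-up visit. No efficacy conclusion, no randomised comparison with placebo and no endpoint defined in SAP 2.3.4 is affected.

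The conclusion assumes that both analytes are sensitive to recent food intake, that the Day 1 sample is normally available as Baseline, and that no unsupplied document imposes or records fasting at Week 72. It is worth correcting because the change is specific and cheap and SAP 10.2 needs reconciling with SAP 2.3.4 in any case.

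**What to change.** In SAP 10.2:

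- Limit change-from-Baseline and shift tables for glucose and triglycerides to Weeks 28 and 52. List the Week 72 values labelled 'fasting not required'. Hematology and the other chemistry parameters can keep their Week 72 tables.
- Flag, rather than bar, any Screening value used as Baseline for these two analytes. Barring it could leave a subject with no Baseline.
- Reconcile the time points with SAP 2.3.4, which ends at Week 52, and remove lipids from the Week 72 summary, since none are collected then.

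In SAP section 12, declare the restriction as a departure from protocol 9.4.2.2, which calls for change from Baseline at every scheduled assessment.

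The cost is a few sentences in the SAP and the loss of Week 72 change and shift tables for two analytes. No endpoint stated in SAP 2.3.4 is lost. Requiring a fast at Week 72 would also align the conditions, but it needs a protocol amendment and would not help samples already taken.

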10.3 Vital Signs

Vital signs measurements including temperature, pulse rate, systolic blood pressure, diastolic blood pressure, and respiratory rate at each scheduled visit and changes from baseline during the treatment period will be summarized by treatment arm. Vital signs will also be presented in a shift table displaying the cross tabulation of the Baseline result category versus the result of the post-treatment period at each scheduled visit. The categories of each vital sign parameters are as below:

All vital signs measurements will be listed by subject.

10.4 12-Lead Electrocardiogram (ECG)

The ECG measurements at each scheduled visit (Baseline and Week 52 Visit) and change from baseline during the treatment period will be summarized by treatment arm.

All ECG measurements and the overall interpretation will be listed by subject. Abnormal QTcF values will be flagged in the listing. QT results for subjects having no reported QTcF values will be transformed to QTcF values and flagged in the listing.

10.5 Physical Examinations

The frequency of subjects with abnormal evaluations of body system findings for physical examinations will be summarized by visit and treatment group; abnormal physical examination findings will also be presented in a by-subject listing.

10.6 Other Safety Parameters

The subjects will be assessed for suicidal ideation and behavior using Columbia-Suicide Severity Rating Scale (C-SSRS) at screening, baseline, and each subsequent visit. C-SSRS contains two categories: (1) Suicidal Ideation (questions 1-5), most severe ideation will also be collected; (2) Suicidal behavior (questions 6-10).

The following outcomes are C-SSRS categories and have binary responses (yes/no). The categories listed below have been re-ordered from the actual scale in an increasing order of severity from 1 to 10 to facilitate the definitions of the comparative endpoints.

Table 6 C-SSRS Outcomes

| Categories |
|--|
| Suicidal Ideation (1-5) |
| 1 – Wish to be dead |
| 2 – Non-specific active suicidal thoughts |
| 3 - Active suicidal ideation with any methods (not plan) without intent to act |
| 4 - Active suicidal ideation with some intent to act, without specific plan |
| 5 – Active suicidal ideation with specific plan and intent |
| Suicidal behavior (6-10) |

| Effective Date: 10-AUG-2020 | Page 44 of 61 |
|-----------------------------|---------------|

| Categories |
|----------------------------------|
| 6 - Preparatory acts or behavior |
| 7 – Aborted attempt |
| 8 — Interrupted attempt |
| Suicidal acts (9-10) |
| 9 – Non-fatal suicide attempt |
| 10 – Completed suicide |

The following are numerical scores derived from the above C-SSRS categories.

- Suicidal Ideation Score: The maximum suicidal ideation category (1-5 on the C-SSRS) present at the assessment. Assign a score of 0 if no ideation is present.
- Suicidal Behavior Score: The maximum suicidal behavior category (6-10 on the C-SSRS) present at the assessment. Assign a score of 0 if no behavior is present.
- Suicidal Ideation or Behavior Score: The maximum suicidal ideation or behavior category (1-10 on the C-SSRS) present at the assessment. Assign a score of 0 if no ideation or behavior is present.

Subjects are also classified into two risk levels:

- Intermediate risk level is indicated by a response of "yes" to Questions 1 to 3 and the absence of a "yes" response to Questions 4 and 5 in suicidal ideation section.
- High risk level is indicated by a response of "yes" to Questions 4 or 5 in the suicidal ideation section, or any positive response in the behavioral section of the C-SSRS.

Change in binary response to the questions from no to yes in any questions will be summarized in a shift table describing baseline vs post-baseline per visit, and worst post-baseline overall. Categorical scores will be analyzed similarly. C-SSRS risk levels are also summarized by visit. Results from the C-SSRS will be listed by subject. Results to Week 28 will be described in the Part 1 analysis, and overall results to Week 52 will be described in the final analysis.

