- 15. Subjects who were hospitalized due to an acute cardiovascular event (such as myocardial infarction, cerebrovascular accident, cardiovascular illness [e.g., angina pectoris], or cardiovascular surgery [such as coronary artery bypass]) within 6 months before Screening.
- 16. Subjects who, in the opinion of the Investigator, will not be reliable participants in the study and those who can confound the results of the study.
- 17. Subjects who have a history of alcohol or drug abuse in the previous year.
- 18. Subjects who have a high risk of suicidality at the Screening assessment based on the Investigator's judgment or, if appropriate, as indicated by a response of "yes" within the last 12 months to Questions 4 or 5 in the suicidal ideation section or any positive response in the behavioral section of the C-SSRS.
- 19. Subjects with any other clinically significant laboratory abnormality, which, in the opinion of the Investigator, will prevent the subject from completing the study or will interfere with the interpretation of the study results.
- 20. Subjects with a known history of allergy or hypersensitivity to any of the inactive ingredients of the Tildrakizumab or placebo formulations.

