8.2.3 Assessment of Suicidal Ideation and Behavior

- The subjects will be assessed for suicidal ideation and behavior at Screening using Screening Columbia-Suicide Severity Rating Scale (C-SSRS), at Baseline (using Baseline C-SSRS), and each subsequent visit using the C-SSRS Since Last Visit version (seeAppendix 18). There are 5 questions relating to levels of suicidal ideation which prompt questioning about suicidal behavior or intensity of ideation, depending on response.
- Subjects acknowledging active thoughts of self-harm but lacking an articulated plan for doing so are classified at the intermediate risk level; those presenting a defined self-harm plan or lacking needed impulse control are judged to be at the high-risk level.
- Subjects who have a high risk of suicidality at the Screening assessment based on the Investigator's judgment or, if appropriate, as indicated by a response of "yes" within the last 12 months to Questions 4 or 5 in the suicidal ideation section or any positive response in the behavioral section of the C-SSRS should not be enrolled in the study.
- Those subjects who develop suicidal ideation during the study rated as high risk according to the above classification must be temporarily discontinued from receiving study treatment and referred promptly for psychiatric evaluation.
- Subjects rated as displaying the intermediate level of suicidal ideation should receive psychological support and be assessed on an individual basis.
- All individuals assessed as exhibiting suicidal behavior, except preparatory acts, must discontinue study treatment permanently. The presence of non-suicidal self-injurious behavior should be assessed on an individual basis.

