© 2008 The Research Foundation for Mental Hygiene, Inc.

SUICIDAL IDEATION				
Ask questions 1 and 2. If both are negative, proceed to "Suicidal Behavior" section. If the answer to question 2 is "yes", ask questions 3, 4 and 5. If the answer to question 1 and/or 2 is "yes", complete "Intensity of Ideation" section below.				
1. Wish to be Dead	Aug to december 12 over 12 out	Yes		
Subject endorses thoughts about a wish to be dead or not alive anymore, or wish to fall asleep and not wake up. Have you wished you were dead or wished you could go to sleep and not wake up?			No	
If yes, describe:				
2. Non-Specific Active Suicidal Thoughts				
General, non-specific thoughts of wanting to end one's life/commit suit oneself/associated methods, intent, or plan. Have you actually had any thoughts of killing yourself?	cide (e.g., "I've thought about killing myself") without thoughts of ways to kill	Yes	No	
If yes, describe:				
3. Active Suicidal Ideation with Any Methods (Not Plan				
	thod during the assessment period. This is different than a specific plan with time, but not a specific plan). Includes person who would say, "I thought about taking an would actually do it and I would never go through with it."	Yes	No	
If yes, describe:				
4. Active Suicidal Ideation with Some Intent to Act, with			.,	
Active suicidal thoughts of killing oneself and subject reports having so definitely will not do anything about them." Have you had these thoughts and had some intention of acting on the	ome intent to act on such thoughts, as opposed to "I have the thoughts but I m?	Yes	No	
If yes, describe:				
 Active Suicidal Ideation with Specific Plan and Intent Thoughts of killing oneself with details of plan fully or partially worker 		Yes	No	
Have you started to work out or worked out the details of how to kill y	ourself? Do you intend to carry out this plan?			
If yes, describe:				
INTENSITY OF IDEATION				
The following features should be rated with respect to the most	severe type of ideation (i.e., 1-5 from above, with 1 being the least severe			
and 5 being the most severe). Ask about time he/she was feeling the most suicidal.			ost	
Most Severe Ideation:		Sev	ere	
Type # (1-5)	Description of Ideation			
How many times have you had these thoughts? (1) Less than once a week (2) Once a week (3) 2-5 times in w	eek (4) Daily or almost daily (5) Many times each day		-	
Duration				
When you have the thoughts, how long do they last?	(A) A 9 hours broost of day			

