3.2 Definition of Baseline Values

Unless otherwise specified, "Baseline" is defined as the last observed value of the parameter of interest prior to the first intake of study treatment (this includes unscheduled visits).

For Nail Pain NRS, the complete observation will be performed on the average score for each visit that will be based on the seven daily scores. The complete score at a given visit will be based on an average of no less than four of the seven prompted valid daily recall observations. No imputation of missing daily recalls will be used, and the change in averaged scores at Baseline and Week 28 will provide the basis for analysis. Hence, baseline NRS will be defined as the average score of the 7 consecutive daily scores leading up to the Baseline Visit (Visit 2); the baseline score will be computed if there are four or more valid scores out of the seven prompted assessments. If a subject missed 4 or more entries during the 7 days before Baseline visit, the Baseline NRS value will be considered as undefined (missing) for the subject.

For numerical variables, change from Baseline will be calculated as the difference between the post-Baseline value and the corresponding Baseline value and calculated as: post-Baseline value — Baseline value. The percent change from Baseline will be calculated as change from Baseline divided by the Baseline value, expressed as a percentage.

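### The C-SSRS shift table in SAP 10.6 sets a history-type Baseline form against 4-to-8-week Since Last Visit forms, so ideation that recurs on items already endorsed is not counted as a change

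*SAP*

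**What the plan says.** Protocol 8.2.3 fixes the form used at each visit: the Screening form at Screening, then "at Baseline (using Baseline C-SSRS), and each subsequent visit using the C-SSRS Since Last Visit version". The notes to the Schedule of Activities say the same.

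SAP 3.2 states that the baseline "is defined as the last observed value of the parameter of interest prior to the first intake of study treatment". For the C-SSRS this is the Week 0 Baseline form. SAP 10.6 then sets the rule: "Change in binary response to the questions from no to yes in any questions will be summarized in a shift table", which compares Baseline with each later visit and with the worst post-baseline result. For the derived ideation and behaviour scores it adds: "Categorical scores will be analyzed similarly". SAP 10.6 does not mention that the forms have different recall periods. SAP 2.3.4 lists change from Baseline in C-SSRS results through Week 52 as a safety endpoint.

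In Protocol Appendix 19, the behaviour column of the Baseline form is headed as lifetime. Its ideation-intensity section tells the rater: "Ask about time he/she was feeling the most suicidal". The Since Last Visit form drops that instruction and heads both its ideation and its behaviour columns with the period since the last visit.

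Exclusion criterion 18 (Protocol 5.2) turns on the investigator's judgement of high risk or, where appropriate, on a yes answer "within the last 12 months to Questions 4 or 5 in the suicidal ideation section", or on any positive behavioural response.

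**The concern.** A shift table shows change only if both of its axes measure the same thing. Here the Baseline axis carries history and the post-baseline axis carries a few weeks. Two kinds of misclassification follow.

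- A subject with past ideation who has it again on study, on the same items, sits in the yes-to-yes cell. That is a new on-study event, but it is not the no-to-yes change that the SAP says it will summarise.
- A subject with past ideation and none on study moves from yes to no. Nothing need have improved; the question has become narrower.

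This matters because the endpoint is itself defined as change from Baseline, and because Protocol 2.2 says that patients with psoriasis have a raised risk of suicidal ideation. With about 48 subjects per arm and few events likely, misplacing one or two recurrences could alter what the table appears to show.

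**Working it through.** The plan gives no figure on this point to reproduce, so the check is one of logic, using the forms and the SAP's rule.

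**Recall periods.** In the Schedule of Activities the C-SSRS is done at Weeks 0, 4, 8, 12, 16, 20, 24, 28, 32, 36, 40, 44 and 52. The gaps are 4 weeks up to Week 44 and 52 − 44 = 8 weeks at the end, longer if a visit is missed. The Baseline form has no such limit.

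**Who can start at yes.** Criterion 18 names Questions 4 and 5 only within 12 months. Past ideation on Questions 1 to 3, and on Questions 4 or 5 more than 12 months ago, can therefore enter unless the investigator judges the risk high. Positive behaviour is excluded, so baseline behaviour answers should be almost all no.

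**Per-question rule.** Questions 1 and 2 are always asked; Questions 3 to 5 only if Question 2 is yes.

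- Possible answer patterns: with Question 2 no, 2 (Question 1 yes or no); with Question 2 yes, 2 × 2³ = 16. Total 18, of which 17 contain at least one yes.
- Pairs of a positive history with a positive on-study form: 17 × 17 = 289.
- A pair registers no change when every on-study yes was already yes at Baseline. By Baseline pattern: Question 1 only, 1 pair; Question 2 without Question 1, 3³ = 27 pairs; Questions 1 and 2 both yes, 8 + 2 × 27 = 62 pairs. Total 1 + 27 + 62 = 90.
- Not counted as a change: 90/289 = 31%. Counted through at least one newly endorsed item: 289 − 90 = 199, or 69%.

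**Maximum ideation score.** Past and on-study levels from 1 to 5 give 5 × 5 = 25 pairs. The on-study level is at or below the past level in 5 + 4 + 3 + 2 + 1 = 15, so 15 show no upward shift and 10 do. Of the 15, 5 are unchanged and 10 shift downward although ideation occurred on study.

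**Examples.** Past yes to Question 1 only, new yes to Question 4 on study: counted. Past yes to Questions 1 to 3, the same three on study: not counted. Past yes to Questions 1 to 3, none on study: score 3 to 0.

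**With the fix.** Counting any post-first-dose yes, whatever the history, captures all 289 pairs.

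**How many subjects.** The documents give no prevalence of past ideation. If it were 5% to 20% (an assumption), 0.05 × 96 = 4.8 and 0.20 × 96 = 19.2, so about 5 to 19 subjects would have an item that starts at yes. That bounds who could be affected; it does not estimate recurrences.

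**The case against.** The best reply is that the events are not lost. Elsewhere in the SAP (10.2 and 10.3) a shift table is a full cross-tabulation. If the same is meant in 10.6, the worst-post-baseline table has a yes-to-yes cell, and its post-baseline margin counts on-study answers split by Baseline. Post-baseline risk levels come from Since Last Visit forms and are summarised by visit. All results are listed. Suicidal ideation is an event of clinical interest (Protocol 8.3.7), and SAP 10.1 summarises and lists such events.

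Much of this stands. A reader might infer that the analysis is blind to on-study ideation; the documents do not support that. Nor do they support the inference that anyone with past ideation can never show a change: the rule works question by question, so escalation to a new item is counted. Nothing in SAP 10.6 says that yes-to-no will be reported as improvement, and any recall effect should be similar in the two randomised arms.

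Two further limits are fair. Lifetime recall is legible only for behaviour, where criterion 18 largely removes the problem. For ideation it is inferred from the instruction about the most suicidal time, which sits in the intensity section and not with the yes/no items; a column heading may also have been lost from the text.

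What the reply does not cure is this. SAP 10.6 names only no-to-yes change and does not say that all cells will be shown. The risk-level summary is by visit, not cumulative. Event-of-clinical-interest tables depend on an event being recorded, whereas the C-SSRS is the systematic instrument. Listings do not compare arms. The one cumulative C-SSRS summary, worst post-baseline, is tied to the mismatched Baseline.

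**Conclusion.** The point holds in a limited form. The rule in SAP 10.6 misclassifies on-study ideation at or below the level of past ideation, and it turns old history without recurrence into a shift produced by recall length alone. Among subjects with past ideation who have it again, 90 of 289 answer patterns register no per-question change and 15 of 25 score pairs show no upward shift; how often these patterns would occur is unknown.

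The conclusion assumes that the Baseline ideation items reach back further than the Since Last Visit items, which the forms suggest but the available text does not state. It also assumes that some subjects with permitted past ideation enrol. It concerns ideation far more than behaviour, and one descriptive safety table only. It is still worth correcting, because it bears on a listed safety endpoint and no planned C-SSRS summary gives a cumulative count by arm that is independent of Baseline.

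**What to change.** In SAP 10.6:

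- State the recall period of the Screening, Baseline and Since Last Visit forms.
- Add the number and percentage of subjects with any post-first-dose yes, separately for ideation and for behaviour, by arm, for Part 1 and for Parts 2 and 3, regardless of Baseline and split by Baseline history (yes/no). The Week 28 form is completed before that visit's injection and so belongs to Part 1. The schedule has no C-SSRS at Week 72, so the second count ends with the End of Treatment form.
- If the shift table is kept, show all cells, label it as history versus on-study, and state that yes-to-no is not to be interpreted as improvement. Apply the same to the derived scores.

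The cost is SAP wording and one re-specified descriptive table. No new data are needed, and no efficacy test, power or alpha changes.
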